### 2.3 Study Aims:

The current study examines the neural response, as well as the cortisol hormonal response to social evaluative stress across the transition to puberty. We use a modified version of the Trier Social Stress Test (TSST) in the MRI scanner (called the Minnesota Imaging Stress Test in Children; MISTiC) to elicit social evaluative stress. In this project, we will randomly assign youth to complete this testing under one of three social buffering conditions: presence of a parent, presence of an experimenter (stranger), or no social support present (standard imaging condition).

The **long-term goal** of our research is to enrich understanding of stress regulation and its role in human development. The **overall objective** of this project is to understand normative processes in stress regulation and their neurobiological correlates as children leave childhood and become more autonomous in adolescence. The **central hypothesis** of this project is that early adolescence is a period of time when parental buffering wanes in efficacy, leaving many youth experiencing a relative dearth of relationships that can provide powerful stress buffers.

**The aim of the current study is to delineate changes in brain activation in response to social buffering by parents over the pubertal transition.**

**Hypothesis #1:** Parental social buffering will result in increased activation in brain regions associated with safety (e.g. vmPFC) and lower activation in brain regions involved in fear and pain (e.g., insula, amygdala, hypothalamus), as well as tighter coupling between the vmPFC and amygdala activity, but these relationships will wane with pubertal development.

**Hypothesis #2:** Neural activity associated with social buffering will mediate the effectiveness of physiological buffering by social partners.

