## 5.0 Procedures Involved

5.1 Study Design: The study design is cross-sectional. 200 target children (11- to 14-year-olds) will be randomly assigned to one of three conditions: (1) no social support (standard MRI scanning condition); (2) presence of a stranger (experimenter); or (3) presence of a parent. Outcome measures will be compared across the three social buffering conditions. Pubertal stage will be included as a continuous variable in analyses of physiological and/or brain responses.

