- Debriefing of participant to reveal deception (no kids evaluating the recording, two judges were also not actually evaluating performance).

5.2 Study Procedures:

**Social Buffering Manipulations:** Will include 3 between-subjects conditions and both sexes. Participants will be randomly assigned to No Social Partner, Stranger/Experimenter, or Parent.

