### 15.3 Statistical Analysis of MRI and non-MRI Outcome Variables:

The following is a list of the analyses that we will perform on the outcome measures. They are classified as to whether they are the primary or mediational analyses. All statistical analyses will be performed in R.

The primary analyses will consist of a series of multiple regression models. For each dependent variable, variation in neural activity, cortisol response, and heart rate response, we will begin by testing the three-way interaction between social buffering condition, sex, and pubertal stage for all outcomes. If the three-way interaction is not significant, we will then examine all two-way interactions. If the two-way interactions are not significant, we will then examine main effects only models. If the three-way interaction is significant, we will not examine any other model. If condition is significant as an interaction or as a main effect, we will examine all pairwise comparisons using Tukey's Honestly Significant Difference test.

Multiplicity of testing. We will correct for multiple comparisons using the Benjamini-Hochberg (BH) correction. The BH method works by controlling the false discovery rate, and relative to the Bonferroni's correction is more powerful, while still adequately protecting against Type I error (Williams, Jones, & Tukey, 1999).

Mediational Analysis. When changes in activity of brain regions differ by condition or condition by pubertal status and we also see condition or condition by pubertal status differences for cortisol, or heart rate, then we will examine whether brain activity differences mediate the neuroendocrine or autonomic differences. This will be examined using path analysis, while controlling for covariates identified in the preliminary

covariate analysis, and will be estimated using the lavaan package in R (Rosseel, 2012).

The significance of all indirect effects will be assessed using bias-corrected 95% confidence intervals (Efron & Tibshirani, 1986), where confidence intervals that are non-overlapping with zero will be considered significant.

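### The only stated follow-up to a condition by puberty interaction is Tukey's HSD, which, read in its usual sense, does not show which conditions differ in puberty slope or whether parental buffering wanes

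*Combined protocol and SAP*

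**What the plan says.** Hypothesis 1 (section 2.3) is about change. Parental presence should raise activity in safety-related regions, lower it in fear and pain regions and tighten vmPFC-amygdala coupling, "but these relationships will wane with pubertal development". Section 5.1 fixes the scale of the moderator: "Pubertal stage will be included as a continuous variable in analyses of physiological and/or brain responses". Section 5.2 gives the design: "Will include 3 between-subjects conditions and both sexes".

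Section 15.3 sets a stepwise sequence. For each outcome, "we will begin by testing the three-way interaction between social buffering condition, sex, and pubertal stage for all outcomes". Then: "If the three-way interaction is not significant, we will then examine all two-way interactions". Main-effects models come last, and a significant three-way term ends the sequence. One follow-up rule covers all of these cases: "If condition is significant as an interaction or as a main effect", then "we will examine all pairwise comparisons using Tukey's Honestly Significant Difference test". The same section adds: "We will correct for multiple comparisons using the Benjamini-Hochberg (BH) correction".

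The documents name no pairwise slope contrast, simple slope, region of significance or condition contrast at a chosen pubertal score. The simple-effects follow-up in section 15.1 separates speech preparation from rest and does not involve puberty.

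**The concern.** With three conditions, the condition by puberty test has 2 df. A significant result says that the puberty slopes are not all equal. It does not say which conditions differ or in which direction, and a slope difference confined to the stranger condition would also trigger it. Hypothesis 1 is narrower: the parent effect is present early in puberty and shrinks later. The follow-up step has to supply that, and the step that is written down is a procedure for group means.

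A team following section 15.3 literally could find a significant interaction and then report comparisons that do not bear on waning. A team that probed the interaction properly would have to choose the contrasts and pubertal scores after seeing the data. That choice would arise across 12 primary imaging outcomes (6 task-related and 6 connectivity-related, section 15.1) as well as cortisol and heart rate.

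**Working it through.** **1. The plan's own figure.** Section 15.2 gives a minimum detectable f² of 0.056 at n=200 and 0.070 at n=160, for the three-way interaction with 12 covariates, alpha .05 and power .80. Take u=2 numerator df and v=n-24 (12 covariates, 11 condition/sex/puberty terms, intercept), with noncentrality f²(u+v+1). Solving for 80% power gives 0.0548 (v=176) and 0.0709 (v=136). Power at the stated values is 0.809 and 0.795, so the figures reproduce. They describe an omnibus interaction, not any follow-up contrast.

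**2. What each contrast estimates.** For parent v none, write the difference at standardised puberty p as δ + γp.
- Averaged over puberty: δ. The sign of γ drops out.
- Slope contrast: γ.
- Contrast at a chosen score p: δ + γp.

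Waning means that γ has the opposite sign to δ. A comparison of means carries no information on that.

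**3. Illustration.** The documents give no allocation ratio, outcome SD or slope size. Assumed: 1:1:1 allocation (200/3 = 66.7 per arm), residual SD 1, standard normal puberty, no covariates or sex terms, and only the parent condition differing. Fading case: δ = -0.4 and γ = +0.4, so the effect is zero at +1 SD. Strengthening case: δ = -0.4 and γ = -0.4.

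The Tukey critical value for three groups is about 3.34/√2 = 2.36. Approximate rejection rates for parent v none, fading case:
- Means at average puberty: SE = √(2/66.7) = 0.173; 0.4/0.173 = 2.31; Φ(2.31-2.36) ≈ 48%.
- Slope: SE ≈ √(2/63.7) = 0.177; 0.4/0.177 = 2.26; Φ(2.26-2.36) ≈ 46%.
- Parent contrast at -1 SD: effect -0.8; SE = √(0.173² + 0.177²) = 0.247; 0.8/0.247 = 3.24; Φ(3.24-2.36) ≈ 81%.

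Simulated rates for parent v none, Tukey-adjusted:

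| Case | Means | Slope | At -1 SD |
|---|---|---|---|
| Fading, all replicates | 47% | 46% | 79-81% |
| Fading, given a significant interaction | 47% | 70% | 89% |
| Strengthening, all replicates | 49% | – | – |

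Because the assumed puberty distribution is symmetric, the true rate for means is the same for fading and strengthening; 47% v 49% is simulation error. A 20,000-replicate repeat gave 45% in both directions for raw means and 47% in both for means at average puberty. For the fading case it gave 46% (slope) and 80% (-1 SD), or 72% and 91% given a significant interaction.

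**4. At the plan's detectable size.** If only the parent slope differs, f² = γ²·(1/3)(2/3), so f² = 0.056 gives γ = √(0.056/0.222) = 0.50. Results at n=200 with 4,000 replicates (an average effect, where present, is -0.50):

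| Case | Omnibus interaction | Means, parent v none | Slopes, parent v none |
|---|---|---|---|
| Fading to zero at +1 SD | 83% | 66% | 68% |
| Strengthening, same average effect | 83% | 64% | 68% |
| Constant buffering, no waning | 5% | 70% | 2% |
| Only the stranger slope differs | 83% | 1% | 2% |

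At n=160, with γ sized to f² = 0.070, the pattern is the same. Means reject 64% when the effect fades, 64% when it strengthens and 72% when it is constant.

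**The case against.** **The plan does test waning.** A reader might infer that it has no such test. The documents do not support that: the two-way step in section 15.3 includes condition by continuous puberty, and that omnibus test addresses moderation. The gap lies in locating and describing an interaction once it is found.

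**The text does not say that means averaged over puberty are compared.** It says only that all pairs are compared by HSD. Reading this as condition means follows the usual sense of the procedure, and Tukey-adjusted slopes or means at set pubertal scores are not excluded. Section 15.2 also refers to an Equation 1 that does not appear in the text available, so the full model cannot be checked. This stands as a limit on the claim. But if slopes or set scores were intended, the plan does not say so.

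**A more dramatic power loss can be produced.** With a slope difference of 0.50 and equal condition means, the comparison of means rejects 2% and the slope contrast about 70%. That is a full crossover, with the parent helping early and harming late by the same amount. Hypothesis 1 says that effects wane, and the earlier work in section 2.2 found no parental effect at advanced puberty, not a reversed one. An effect that fades to zero has a non-zero average, so the crossover should not be used to size this problem.

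**In the fading case the slope contrast is not more powerful.** Over all replicates it rejects 46%, against 47% for means. This also stands: the case for change rests on answering the right question.

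**Conclusion.** The concern holds in a limited form. Moderation by puberty is tested, but the single stated follow-up, in its usual sense, cannot show which conditions differ in slope or tell waning from strengthening. For an average parent effect of -0.4 SD it rejects at about the same rate (47% and 49%) whichever way the effect moves with puberty. Given a significant interaction in the fading case, the contrasts that bear on Hypothesis 1 reject about 70% (slope) and 89% (-1 SD of puberty), against 47% for means. All these percentages rest on the assumed allocation, unit residual SD, normal puberty and absence of covariates. The argument in step 2 of the working does not depend on those values, only on reading HSD as a comparison of means. The omnibus test is unaffected, so this is a correction that should be made, not a flaw that invalidates the analysis.

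**What to change.** Amend section 15.3 as follows.
- After a significant condition by puberty term, compare puberty slopes pairwise between conditions. Also estimate condition differences at two prespecified pubertal scores, one early and one late, with the scores named in the plan. Apply Tukey adjustment within each set.
- If the three-way term is significant, do the same within each sex, because the plan then fits no simpler model.
- Keep Tukey's HSD on means for the main-effects model.
- State how these Tukey adjustments combine with the Benjamini-Hochberg correction in the same section.

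The cost is a change of wording and a few more contrasts to report. The data, sample size and fitted model stay the same.

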**Stressor Paradigm:** MISTiC paradigm while the child is lying in the MRI scanner; includes two judges (one male, one female). After consent, youth are separated from their parents and taken for completion of questionnaires (approximately 20 minutes). Youth are taken to a private changing room to change into hospital scrubs prior to moving to the MRI scanner. An MRI-safe respiration belt and pulse oximeter and/or EKG electrodes are positioned for autonomic assessment and the child is given ear plugs, a button response box for math task, and an emergency call button. Youth rest and/or watch a video of their choosing during structural MRI sequences (6-10 minutes), then lie quietly with eyes open for a 5-minute scan with no video or audio material. They are then given an overview of the speech task and are told that they have 5 minutes to prepare. MRI data are collected during the 5 minutes of speech prep, following which the child is introduced to two judges who are visible on the child's video screen and who ask the child to perform their 5 min speech. No MRI data are collected during speech performance. At the end of the speech, the judges give the child instructions for the math performance section, and the child performs multiple-choice math problems that appear on the video screen using the button response box. MRI data are collected during math performance and judges remain visible on the screen during math performance. Following the judged math, judges leave the screen and youth rest or watch a video for 10 minutes during diffusion scanning. Finally, children perform another set of multiple-choice math problems with no judges present (photo of the same judges turned away) while MRI data are collected. Children are removed from the scanner and immediately complete a stress questionnaire and a debriefing session. Saliva samples are collected every 10-20 minutes throughout the session, including between scan segments, to assess dynamic changes in stress-related hormones. In the scanner, this involves handing a long collection sponge to the child which hangs out of the mouth to avoid any possibility of choking since the child is lying supine. We have used this method successfully in a previous study collecting saliva in the scanner environment. Following debriefing, the child will change back into their own clothing and return to the lobby to complete additional questionnaires for 30 min while being sampled for cortisol every 10 min.

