Task-based analysis: Math under social evaluative stress In first level analyses (single subject, single-run), math performance will be modeled for each participant using a voxel-wise multiple regression analysis with a task predictor (math trials vs. blank trials), 24 regressors for head motion (Satterthwaite et al., 2013) and additional regressors to model censored data points (motion spikes). In subsequent analyses, we will explore the utility of including other time varying individual differences variables (e.g., heart rate, respiration) that are known to contribute to the BOLD signal. However, since these measures are expected to vary by stress condition, removing the effects of these physiological variables may unintentionally remove effects of interest. Particular care will be taken to reduce the confound of head motion by censoring (identifying as artifact) any data point with absolute motion greater than 2 mm (1 voxel) or a framewise displacement greater than 0.5 mm, as well as the immediately preceding and following data points. Data points with DVARS values exceeding the

individual's 75th percentile plus two times the interquartile range will also be censored. Participants with more than 25% of data points censored for artifact will be excluded from further analyses.

Second level analyses (single-subject, multiple runs) will test the within-subject contrast of math performed with judges (social evaluative stress) relative to math performed alone (without social evaluation) to identify brain regions differentially activated by social evaluative stress. Based on prior literature, we will examine activation in 5 *a priori* regions of interest, including "pain-related" brain regions (dorsal anterior cingulate [dACC], left and right anterior insula) and "safety-related" or regulatory brain regions (ventromedial prefrontal cortex [vmPFC], and left and right dorsolateral prefrontal cortex [dlPFC]). For each subject, the mean percent change in MR signal (averaged across voxels) between judged math and math alone will be extracted from each of these 6 regions. This analysis will generate the 6 task-related brain activation outcome variables (listed in section 4.3) for each participant.

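### For the task-based brain measures, Hypothesis 2's mediator includes a run acquired after part of the cortisol outcome, so a positive result cannot by itself be read as brain activity driving cortisol

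*Combined protocol and SAP*

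**What the plan says.** Hypothesis 2 (section 2.3) is directional: neural activity is to mediate physiological buffering. Section 15.3, Mediational Analysis, carries this out. When brain activity and cortisol (or heart rate) both differ by condition, or by condition and puberty together, "then we will examine whether brain activity differences mediate the neuroendocrine or autonomic differences". The tool is a path model with bias-corrected 95% intervals for the indirect effect.

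The task-based brain variable is defined in section 15.1: for each region of interest, "the mean percent change in MR signal (averaged across voxels) between judged math and math alone will be extracted".

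Section 5.2, Stressor Paradigm, fixes the order of events:
- Preparation: "They are then given an overview of the speech task and are told that they have 5 minutes to prepare".
- Speech: the judges appear, "who ask the child to perform their 5 min speech".
- Judged math: "MRI data are collected during math performance and judges remain visible on the screen during math performance". Its length is not given.
- Gap: "Following the judged math, judges leave the screen and youth rest or watch a video for 10 minutes during diffusion scanning".
- Comparison run: "Finally, children perform another set of multiple-choice math problems with no judges present".

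No counterbalancing and no math run before the stressor is described. Saliva is taken every 10 to 20 minutes, also between scan segments, and then every 10 minutes for 30 minutes after debriefing. Section 5.2, Stress Hormones, reduces these samples to one AUCi per child, with no window tied to the scans.

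**The concern.** A mediator should be measured before the outcome that it is said to cause. Here one of the two runs in every task mediator comes after some of the cortisol samples that make up the outcome. If buffering works, cortisol already differs by arm at that point. Any effect of cortisol or lingering stress on the alone run then enters judged-minus-alone with its sign reversed, and makes that score correlate with cortisol even if the judged run does not.

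Randomization does not resolve this. It protects the effect of condition on each variable, but not the path between brain and cortisol. Section 15.3 specifies no time ordering, no adjustment for cortisol already present, no reverse-path check and no analysis of the two runs separately. Section 15.1 does plan separate-period follow-up for connectivity, on the ground that a difference score can hide direction, but gives no equivalent for the task contrast. What is at stake is whether a positive task-based result can support the direction stated in Hypothesis 2.

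**Working it through.** **Timing (section 5.2).** Let x be the unstated length of judged math.
- Start of math alone, from the start of preparation: 5 + 5 + x + 10 = 20 + x minutes.
- From the start of the judged speech: 5 + x + 10 = 15 + x minutes.
- With x assumed between 0 and 10, these are 20 to 30 and 15 to 25 minutes, plus untimed introductions, instructions and saliva collection.
- With saliva every 10 to 20 minutes, at least one sample falls between the start of preparation and math alone.
- Judged math starts at least 5 + 5 = 10 minutes after preparation begins.
- The speech-preparation scan and the earlier resting scan, which form the connectivity mediators, precede both math runs.

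**Mechanism.** The plan gives no figure to reproduce, so the effect must be modelled. Let C be cortisol in SD units, lowered by d in the parent arm; J the judged run, unrelated to C; and A the alone run, shifted by c per SD of cortisol. The mediator is D = J − A. Scale D so that its SD without carry-over is 1.
- Spurious condition → D path: a = c × d.
- Spurious D → cortisol path given condition: b = −c / (1 + c²).
- Spurious indirect effect: a × b = −c²d / (1 + c²). As a share of the total effect −d this is c² / (1 + c²).
- For c = 0.1, 0.2, 0.3 the shares are 0.01/1.01 = 1.0%, 0.04/1.04 = 3.8% and 0.09/1.09 = 8.3%. The simulated shares at d = 0.5 were 1.1%, 3.9% and 8.2%.

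**False-positive rates.** 2,000 simulated trials per setting, n = 200, one third in the parent arm, d = 0.5 to 0.8, correlation 0.5 between runs, no brain-to-cortisol path and no condition effect on the judged run. The test requires both paths to be significant at .05.

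| Cortisol acting on the alone run | c = 0.1 | c = 0.2 | c = 0.3 |
|---|---|---|---|
| Same as AUCi | 2–3% | 7–14% | 15–34% |
| Early part, correlation 0.7 with AUCi | 1% | 4–9% | 13–26% |
| Early part, correlation 0.4 with AUCi | 1% | 2–4% | 6–12% |

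A second set-up, with independent runs and an interval for the product a × b in place of the joint test, gave 1.6%, 6.1% and 12.0% at d = 0.5, and 2.2%, 11.4% and 25.3% at d = 0.8. At c = 0 it gave 0.0% to 0.2%.

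**If condition also affects the judged run.** Hypothesis 1 predicts such an effect. With the second set-up, a parent effect of +0.5 on the judged run and d = 0.5, false mediation was 3.5%, 24.1%, 70.5% and 93.8% for c = 0, 0.1, 0.2 and 0.3. With the judged run alone as mediator, and a parent effect of +0.5 or −0.5, it was 4.4% to 5.6% throughout. That last result assumes that cortisol does not yet act on the judged run.

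**The case against.** The strongest reply is that the mechanism is imported. The documents give no cortisol time course and do not say that cortisol changes the MR signal during math. That stands: the carry-over sizes are assumptions, and without carry-over there is no excess. What the documents do establish is that the order of measurement leaves the alternative open and that the model has no means of testing it.

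A reader might infer that the alone run follows most of the cortisol outcome. The documents do not support that. If each math run takes 5 minutes and debriefing 10 (both assumed), 5 + 5 + 5 + 10 = 25 minutes of the post-onset window precede the alone run, and 5 + 10 + 30 = 45 minutes follow its start.

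A reader might also take the brain-to-cortisol path by itself, which is falsely significant in 27%, 80% and 98% of trials at c = 0.1, 0.2 and 0.3. That is one path, whereas section 15.3 tests the indirect effect. Section 15.3 also opens mediation only when brain activity and cortisol both differ. Adding that gate at .05 gives overall rates of about 1%, 4–9% and 8–23%. An approximate Benjamini-Hochberg threshold (rank 2 of 14, assumed) gives 0.1–0.3%, 1–3% and 2–8%. The gate makes the event rarer but not easier to interpret: among trials that pass the .05 gate, about 28%, 71–79% and 98% show false mediation.

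Direction matters too. Positive carry-over raises judged-minus-alone in the parent arm. That agrees with Hypothesis 1 for safety regions such as vmPFC and opposes it for insula. The artefact therefore does not favour the hypothesis everywhere.

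Finally, section 15.3 refers to the exploratory nature of the mediation analysis when discussing its power, and warns there of concluding mediation that is not present. That warning concerns power, not timing, and this analysis is the planned test of Hypothesis 2.

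**Conclusion.** The point holds as a limit on interpretation. Every a priori task mediator subtracts a run acquired at least 20 minutes plus the judged-math time after preparation begins, while AUCi contains earlier saliva. A positive task-based result therefore cannot, by itself, be read as brain to cortisol.

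The size is uncertain. With no condition effect on the judged run, and before the gate, the joint test is falsely positive in about 1% to 34% of trials for assumed carry-over of 0.1 to 0.3 SD per SD. The rate depends also on the cortisol effect and on how closely early cortisol tracks AUCi. It is higher if condition also affects the judged run.

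A reader might go further and conclude that judged-minus-alone should be dropped as mediator. The documents do not support that: it is the contrast that isolates social evaluation, and replacing it would be a trade-off rather than a correction. The connectivity mediators are not affected.

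**What to change.** In section 15.3, Mediational Analysis, keep judged-minus-alone as the planned task mediator and add:
- mediation models for cortisol using judged-math and alone-math activation separately, each taken from its own first-level math-versus-blank estimate, which section 15.1 already fits. This mirrors the separate-period follow-up planned for connectivity;
- a rule that brain-to-cortisol mediation is claimed from the task measures only if the judged-run model supports it, and that the result is otherwise reported as an association.

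The speech-preparation connectivity mediators stay as planned.

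The cost is a few extra models and a few sentences; no new data are needed. There are two limits. Judged-versus-blank activation includes general math activity and is less specific to social evaluation. Overlap with cortisol is reduced rather than removed, because judged math itself starts at least 10 minutes after preparation begins.

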Power Analysis for the Mediational Analysis: To assess power to detect mediation, we performed a Monte Carlo-based power analysis using simulated data. We varied the parameter values to roughly correspond to Cohen's criteria for small, medium, and large effects. This resulted in a total of 27 conditions, which we examined at our target sample size of 200. Each condition was replicated 2000 times and we calculated empirical power, which we defined as the proportion of times out of 2000 where we rejected the null hypothesis at  $\alpha = .05$ . Given the exploratory nature of this analysis and to simplify the simulation for the power analysis, we omitted covariates and did not vary the effects for the other condition contrasts (i.e., they were always fixed to 0). Next, we fit a path model using the lavaan package in R.

Our findings suggest that in order to detect mediation, the effect of condition on the mediator must be large and the effect of the mediator on the outcome must be medium or large. In addition, if the effect of condition on the outcome is not large, but small or medium sized, then we will be underpowered and would likely conclude complete mediation, when mediation may only be partial or non-existent. Based on this power analysis, it is likely that the MDES for the moderated mediation models will need to be at least medium to large as well.

Missing data. Because we will replace participants who do not come in for session 2 after doing session 1 (which is rare in our experience), we should have 200 completed participants. Missing data, however, could arise from problems in obtaining good imaging data. Participants also often fail to fully complete questionnaires and/or refuse to provide information on household income. If there is missingness in any of the dependent or independent variables, multiple imputation will be used (Little & Rubin, 2014; Peng, Harwell, Liou, & Ehman, 2006; Schafer & Graham, 2002). Variables related to the missingness and the variables missing data will be included in the missing data model. In the event that missingness is not at random (MNAR), we will investigate the use of models for non-ignorable missing data.

**15.4 Data Integrity:** Questionnaire data will be double-entered to reduce the likelihood of errors in data entry. Biospecimen data will be assayed in labs

that have standard quality control procedures. MRI data reviewed for raw data quality and artifact detection.

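### Hypothesis 2 is tested only after condition effects appear in both brain and physiology, but the mediation power leaves that requirement out

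*Combined protocol and SAP*

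**What the plan says.** Section 2.3 lists mediation as the second of two numbered hypotheses: "Neural activity associated with social buffering will mediate the effectiveness of physiological buffering by social partners".

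Section 15.3 (Mediational Analysis) makes the test conditional on two findings. The brain side reads "When changes in activity of brain regions differ by condition or condition by pubertal status"; the physiology side adds "and we also see condition or condition by pubertal status differences for cortisol, or heart rate". If both are met, "then we will examine whether brain activity differences mediate the neuroendocrine or autonomic differences". The decision rule is then "The significance of all indirect effects will be assessed using bias-corrected 95% confidence intervals", judged by exclusion of zero. No test of Hypothesis 2 outside this route is planned.

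The mediation power paragraph describes a different sequence. On the simulated effect sizes it says "This resulted in a total of 27 conditions, which we examined at our target sample size of 200". Empirical power is "the proportion of times out of 2000 where we rejected the null hypothesis" at 0.05. Covariates were left out and the other condition contrasts were fixed at zero. The conclusion is qualitative: "in order to detect mediation, the effect of condition on the mediator must be large", and the mediator-to-outcome effect medium or large. The paragraph prints no power value and no parameter value, and it mentions neither the two prior findings, nor BH, nor the loss of scans.

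**The concern.** With one mediator, the total effect of condition on physiology is the product of the two paths plus any direct effect. When the direct effect is small or absent, that total is smaller than either path and its test is the weakest link. An indirect effect can be tested validly without a significant total effect, so requiring one discards datasets in which the indirect test would have succeeded.

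Two things are at stake. The stated detectability belongs to a procedure that will not be run. And if Hypothesis 2 is never tested, a reader cannot tell whether mediation was absent or the total effect was merely too small to reach significance.

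**Working it through.** **Inputs from the documents.** Three conditions and 200 children (5.1); a two-sided 0.05 test of the indirect effect (15.3); 12 brain outcomes, 6 task and 6 connectivity (15.1); possible loss of 40 scans, leaving 160 (15.2); BH correction with no family named (15.3).

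**Assumptions.** Equal arms, with one arm differing from the other two. Condition effects 0.2/0.5/0.8 SD and mediator-to-outcome path 0.1/0.3/0.5 for small/medium/large. The entry sentence does not say significant; I read it that way because the primary-analysis steps before it turn on significance. The indirect effect is tested by joint significance of both paths, standing in for the bias-corrected interval.

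**The plan's own result.** There is no number to reproduce, only the pattern. With four arms on this scale the pattern is matched exactly. With three arms a medium condition-to-mediator effect also reaches 0.81-0.83. If 0.1/0.3/0.5 is used for every path, the need for a large effect holds with three arms (0.81-0.83 against 0.40-0.41). The paragraph does not say how many arms it simulated.

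**Chance that the requirement is met.** Model: M = a·D + e1, Y = c'·D + b·M + e2, residual SDs 1. The total effect is T = ab + c' and the within-arm variance of Y is 1 + b². For the 2-df condition test, the noncentrality is λ = N·(1/3)(2/3)·T²/(1 + b²), and N·(2/9) = 44.44 at N = 200.

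Brain side, a = 0.8: λ = 44.44 × 0.64 = 28.4, so it passes more than 99% of the time. Almost all the loss is on the physiology side. For a = 0.8, b = 0.3:

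| Direct effect c' | T | λ | Physiology test passes | Simulated power without → with the requirement |
|---|---|---|---|---|
| 0 | 0.24 | 44.44 × 0.0576 / 1.09 = 2.35 | 0.26 | 0.98 → 0.25 |
| 0.2 | 0.44 | 44.44 × 0.1936 / 1.09 = 7.89 | 0.70 | 0.99 → 0.68 |
| 0.5 | 0.74 | 44.44 × 0.5476 / 1.09 = 22.3 | 0.99 | 0.98 → 0.97 |

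Setting the total within-arm SD of Y to 1 instead drops the 1.09; the first two rows then give power with the requirement of 0.28 and 0.73. For b = 0.5 and c' = 0, λ = 44.44 × 0.16 / 1.25 = 5.69 and the pass rate is 0.55 (power 0.67 on the other scaling, against 1.00 without the requirement).

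**Across the grid.** Reading the 27 conditions as 3 × 3 × 3 with c' small, medium or large (three arms, N = 200, 0.05), power is at least 0.80 in 12 cells without the requirement and in 5 with it. In the six cells that the plan calls detectable, the requirement is met 0.74-1.00 of the time. If every path uses 0.1/0.3/0.5, the corresponding range is 0.27-0.85. The pass rate follows the total effect: 0.19-0.21 at total d = 0.2, 0.85-0.86 at 0.5, and 1.00 at 0.8.

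**BH and scan loss.** With BH over 14 outcomes (12 brain, cortisol, heart rate; 1 to 6 brain outcomes affected, brain outcomes independent), the pass rate for a = 0.8, b = 0.3 is 0.10-0.19 at c' = 0 and 0.47-0.66 at c' = 0.2. At N = 160 these become 0.06-0.16 and 0.34-0.50.

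**Selection.** Among datasets that meet the requirement, the mean indirect effect is inflated by about 0-15% at N = 200.

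**The case against.** The strongest defence is that Hypothesis 2 concerns what mediates a buffering effect, so looking for a mediator only once buffering has been seen fits its wording. Section 15.3 also separates mediational from primary analyses and calls the former exploratory. That stands as a reason to label the analysis secondary or exploratory. It does not make a significant total effect necessary for the test, and it does not make the power paragraph describe the planned procedure.

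The actual requirement is also wider than the one simulated. Cortisol or heart rate can satisfy it, and so can a condition-by-puberty difference, which Hypothesis 1 expects. With equal effects on two physiology outcomes, the chance that at least one pair is tested rises from 0.71 to 0.91 (a = 0.8, b = 0.3, c' = 0.2). This narrows the loss. The interaction route was not fully simulated and has its own cost: at the plan's detectable f² of 0.056 one interaction test has power 0.81, so two independent ones have about 0.81² = 0.66 (0.48 at N = 160).

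The plan does admit low power when the condition effect on the outcome is small or medium. That warning is about mistaking partial or absent mediation for complete mediation. It takes for granted that the model has been fitted.

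A reader might infer that the requirement usually blocks the test. The documents do not support that. Full mediation is the worst case and, on the natural reading of the 27 conditions, zero direct effect is not among those simulated. Of the 12 cells with power of at least 0.80 without the requirement, only one meets it less than half the time (0.49).

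**Conclusion.** The mismatch is in the text: the planned test of Hypothesis 2 has a two-sided entry requirement, and the stated power omits it. The consequence depends on the total effect on physiology. For a large condition-to-mediator and a medium mediator-to-outcome effect, power falls from about 0.98 to 0.25 with no direct effect and to about 0.68 with a small one. The loss is slight once the direct effect is medium or large.

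These figures rest on assumed effect sizes, equal arms, one outcome of each kind and unadjusted main-effect tests. BH and N = 160 push them down; a second physiology outcome or the interaction could raise the chance of testing. Two further inferences go too far: that a printed power value is wrong (none is printed), and that reported indirect effects would be grossly exaggerated (the inflation is modest). The primary analyses are unaffected. The point should be settled before analysis because it decides whether an absent Hypothesis 2 result can be interpreted.

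**What to change.** Preferred: in 15.3, name a short list of brain outcome × (cortisol, heart rate) pairs, estimate each indirect effect whether or not the separate condition tests are significant, apply BH over that list, and label the results secondary or exploratory. State that the mediation power refers to this unconditional test.

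Alternative: keep the requirement, say that it means statistical significance and whether before or after BH, and rerun the mediation power with the requirement, BH, three arms and N = 160 included, printing the parameter values and the resulting power.

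Either is a change to analysis text and, for the second, a rerun of the simulation; no new data are needed. The price is more indirect effects in the BH family under the first option, or a less favourable stated power under the second.
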